## 8.5. Disease Characteristics

Oncology history will be summarized descriptively by cohort using the Safety analysis set and for Efficacy evaluable analysis set for the following:

- Initial disease diagnosis (histopathologic diagnosis)
- Time (months) since initial disease diagnosis (histopathologic diagnosis) to first dose date
- Stage at diagnosis (0, 1, 2, 3, 4)
- Cancer stage at enrollment (TNM staging) (0, 1, 2, 3, 4)
- Histopathology (urothelial cancer, large cell neuroendocrine tumor of lung, HRD positive endometrial, HRD positive biliary tract, HRD positive breast TNBC, HRD positive HR+HER2-, HRD positive pancreas, HRD positive gastric/esophageal solid tumor, other)
- Mutation type (germline, somatic, unknown) for HRD-positive tumor agnostic malignancies cohort only

Time since initial disease diagnosis (months) = (first dose date – date of initial disease diagnosis + 1)/30.4375. Partial dates for initial disease diagnosis will not be imputed, and time since initial diagnosis will be set to missing.

Planned summaries for prior oncology treatments including prior anti-cancer mediation, prior anti-cancer radiotherapy, prior anti-cancer procedure or surgery are described in [Section 8.7](#).

All disease characteristics will be included in by-participant data listing using Safety analysis set.

## 8.6. Medical History

Medical conditions collected on the Medical History page of the CRF will be coded using the Medical Dictionary for Regulatory Activities (MedDRA) version 25.0. Summary of medical history by system organ class (SOC) and preferred term (PT) will be provided using the Safety analysis set by cohort and across cohorts. A participant will only be counted once within a particular SOC (PT) even if he/she has multiple conditions/diseases in the same SOC (PT). Summary results will be ordered by descending frequency of SOC and PT within each SOC. If the frequencies tie, an alphabetic order will be applied.

A listing of medical history will be provided with the start date, ongoing (yes or no), and the end date, if not ongoing.

Jazz Pharmaceuticals, Inc.

JZP712-201 Statistical Analysis Plan - Protocol Amendment

2

## 8.7. Prior Anti-Cancer Therapy

Prior anti-cancer therapy is defined as those taken by the participant prior to the administration of study treatment. Prior anti-cancer therapy, including systemic therapy, radiotherapy, and procedure or surgery, will be summarized descriptively by cohort for the safety analysis set.

### 8.7.1. Prior Systemic Anti-Cancer Therapy

Prior systemic anti-cancer therapy will be coded to Anatomical Therapeutic Chemical (ATC) Level 4 and PT using the World Health Organization Drug Dictionary (WHODrug) version Mar 2022.

For prior systemic anti-cancer therapy, the following summary results will be prepared:

- Number and percentage of participants with at least one prior systemic anti-cancer therapy
- Number and percentage of participants with 1, 2, 3, 4, and  $\geq 5$  previous lines of therapy
- Number of maximum number of regimens of prior systemic anti-cancer therapy
- Time (months) from completion of the most recent prior systemic anti-cancer therapy to study treatment ( $< 3, \geq 3 - < 6, \geq 6$  months), which is calculated as (date of first dose of the study treatment – date of last dose of the most recent prior systemic anti-cancer therapy + 1) / 30.4375.
- Characteristics of the most recent prior systemic anti-cancer therapy: type of prior systemic anti-cancer therapy, best response, reason therapy ended, and time (months) from completion of the most recent prior systemic anti-cancer therapy to progression/recurrence [calculated as date of progressions/recurrence – date of last dose of the most recent prior systemic anti-cancer therapy + 1) / 30.4375].

All prior systemic anti-cancer therapy will be presented in a participant listing using Safety analysis set. Listing will include regimen number, route, start/stop date (or ongoing), best overall response (and date), progressive disease date, and reason therapy ended.

### 8.7.2. Prior Anti-Cancer Radiotherapy

The number and percentage of participants with at least one prior anti-cancer radiotherapy will be summarized by cohort using Safety analysis set.

All prior anti-cancer radiotherapy will be presented in participant listing using Safety analysis set. Listing will include treatment intent, start/stop date, and setting.

### 8.7.3. Prior Anti-cancer Procedure or Surgery

Prior anti-cancer procedure or surgery will be coded to SOC and PT using MedDRA version 25.0.

The prior anti-cancer procedure or surgery will be summarized by presenting the number and percentage of participants by PT and SOC. Participants with the same procedure or surgery

Jazz Pharmaceuticals, Inc.

JZP712-201 Statistical Analysis Plan - Protocol Amendment

2

reported multiple times will only be counted once for that PT or SOC. Summary results will be ordered by descending order of incidence of SOC and PT within each SOC. If the frequencies tie, an alphabetic order will be applied.

All prior anti-cancer procedure or surgery will be presented in a participant listing including intent for procedure or surgery, date, and result.

## 8.8. Subsequent Anti-Cancer Therapy

Subsequent anti-cancer therapy is defined as an anti-cancer therapy administered after the discontinuation of the study treatment. Number and percentage of participants receiving subsequent anti-cancer therapies, where categories include subsequent systemic therapy, subsequent surgery for cancer treatment, and subsequent radiotherapy for cancer treatment, will be summarized descriptively by cohort for the Safety analysis set. Summary results will include:

- Number and percentage of participants with at least one subsequent anti-cancer therapy
- Number and percentage of participants by type of therapy
- Number and percentage of participants with 1, 2, and  $\geq 3$  subsequent anti-cancer therapy (agents)
- Number of maximum number of regimens (agents) of subsequent systemic anti-cancer therapy

All subsequent anti-cancer therapies will be presented in participant listing using Safety analysis set. Listing will include therapy type, regimen number, start/stop date (or ongoing), dose and units, progressive disease date.

## 8.9. Prior and Concomitant Medications

Prior and concomitant medications will be coded to ATC level 4 and PT using WHODrug version Mar 2022.

Medications taken and stopped prior to the first dose of study treatment are denoted “Prior”. Medications taken prior to the first dose of study treatment and continuing beyond the first dose of study treatment or those medications started on or after the first dose of study treatment but within 30 days of last dose received (the 30-day safety window) are denoted “Concomitant”.

Medication with start date/time being partially or completely missing will be assumed to be concomitant if it cannot be shown that the medication was not administered during the treatment period.

The prior medications will be summarized by presenting the number and percentage of participants by PT and ATC level for each cohort using Safety analysis set. Participants taking the same medication multiple times will only be counted once for that PT or ATC level. Each summary will be ordered by descending order of incidence of ATC level and PT within each ATC level. If the frequencies tie, an alphabetic order will be applied.

Concomitant medications will be summarized in a similar way.

Jazz Pharmaceuticals, Inc.

JZP712-201 Statistical Analysis Plan - Protocol Amendment

2

All prior and concomitant medications will be presented in participant listing using Safety analysis set.

## **8.10. Concomitant Procedures**

Medical or surgical procedures that started after the first dosing date of the study treatment and within 30 days of the last dose received (the 30-day safety window) are denoted “Concomitant”.

Concomitant medical or surgical procedures will be classified using the MedDRA version 25.0.

The concomitant medical or surgical procedures will be summarized by presenting the number and percentage of participants by PT and SOC. Participants having the same medical or surgical procedure multiple times will only be counted once for that PT or SOC. Each summary will be ordered by descending order of incidence of SOC and PT within each SOC. If the frequencies tie, an alphabetic order will be applied. Results will be presented by cohort using Safety analysis set.

All concomitant medical or surgical procedures will be presented in participant listing using Safety analysis set.

## **9. EFFICACY**

All efficacy analyses will be performed using the Efficacy-Evaluable Analysis Set, separately for each of the 3 cohorts, unless otherwise specified.

Primary analysis of objective response rate (ORR) will be based on the investigators' assessment, unless noted otherwise.

Alpha ( $\alpha$ ) for the confidence intervals (CI) will be the two-sided 0.05. CIs for all efficacy endpoints will be at the two-sided 95% level. Point estimates and confidence bounds for efficacy endpoints will be rounded to the second decimal place.

A by-participant listing of efficacy results will be presented for each of the cohorts including treatment duration, progression date, death date, and all the other efficacy endpoints.

### **9.1. Primary Efficacy Endpoint and Analysis**

#### **9.1.1. Primary Analysis**

The primary efficacy endpoint is the objective response rate (ORR).

Best overall response (BOR) is defined as the best response recorded between the date of the first dose of study treatment and the date of objectively documented progression per RECIST v1.1, or the date of subsequent anticancer therapy, death due to any cause, loss to follow-up, or study discontinuation, whichever occurs first. Best overall response (BOR) will be determined programmatically in the analysis of the study results as the best timepoint response that a participant achieves during the study (recorded between the date of the first dose of study treatment and the date of objectively documented progression per RECIST v1.1), with the

Jazz Pharmaceuticals, Inc.

JZP712-201 Statistical Analysis Plan - Protocol Amendment

2

response ranked according to the following order (from best to worst): complete response (CR) > partial response (PR) > stable disease (SD) > progressive disease (PD).

The first post-baseline tumor imaging assessment should occur 6 weeks (+/- 7 days) from the first dosing date. A response of SD can only be made after the participant is on-study for a minimum of 35 days from the date of the first dose. The number and percentage of participants in each category of BOR (CR, PR, SD, PD, not evaluable [NE]) will be presented by each cohort.

The ORR is defined as the proportion of participants whose BOR is investigator-assessed confirmed CR or PR using the RECIST v1.1. The ORR will be summarized by a binomial response rate for each cohort and its corresponding two-sided 95% exact CIs using the Clopper and Pearson method ([Clopper 1934](#)).

The calculation of the ORR and its corresponding two-sided 95% exact CIs will be carried out using the PROC FREQ procedure with the exact binomial option in SAS version 9.4.

A by-participant listing of best overall response will be presented by each cohort including best overall response and dates of CR/PR/progression.

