9.4.2. Primary Endpoint(s)

Best overall response is defined as the best response recorded between the date of first dose and the date of objectively documented progression per RECIST v1.1, or the date of subsequent anticancer therapy, death due to any cause, loss to follow-up, or study discontinuation, whichever occurs first. BOR will be determined programmatically in the analysis of the study results.

The ORR is defined as the proportion of participants whose BOR is investigator-assessed confirmed CR or PR using the RECIST v1.1 criteria. ORR will be summarized by a binomial response rate for each cohort and its corresponding two-sided 95% exact CIs using the Clopper-Pearson method (Clopper, 1934).

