9.5. Interim Analysis

Review of the safety and efficacy data will be performed by the sponsor on an ongoing basis in this study. Assessment of the observed responses will be performed after enrollment of approximately 12 and 20 efficacy-evaluable participants for treatment benefit. If no confirmed response per RECIST v1.1 is observed in approximately the first 12 evaluable participants of a cohort, the recruitment of participants in that cohort will be stopped. If there are ≤ 3 confirmed responses in the first 20 evaluable participants of a cohort, the recruitment of participants in the cohort will be stopped. There will be no pause in enrollment during the interim analysis of the first 12 evaluable participants of a cohort, and the futility boundary will be adjusted based on the actual number of participants at each stage.

Interim futility monitoring will be implemented through the BPP approach with the prior distribution for ORR assumed to be Beta (0.5, 0.5). Table 10 has the operating characteristics for futility of stopping at 12 and 20 participants. If no response is observed in the first 12 participants of a cohort, there is an 89% posterior probability that the actual response rate is

no more than 10%. If there are ≤ 3 responses in the first 20 participants of a cohort, there is a 70% posterior probability that the actual response rate is no more than 20%.

Table 10: Posterior Probability for Interim Futility Monitoring

No Participants	Futility Stopping	Prob ($\theta \leq 10\% r, n$)	Prob ($\theta \leq 15\% r, n$)	Prob ($\theta \leq 20\% r, n$)
12	0	89%	95%	98%
20	1	76%	91%	97%
20	2	46%	72%	87%
20	3	21%	47%	70%

θ = True response rate; r = the observed responses; n = the number of participants

The SAP will describe the planned interim analyses in greater detail.

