#### 5.5. Interim Analysis

Review of the safety and efficacy data will be performed by the sponsor on an ongoing basis in this study.

Assessment of the observed responses will be performed after enrollment of approximately 12 and 20 efficacy-evaluable participants for treatment benefit. If no confirmed response per RECIST v1.1 is observed in approximately the first 12 evaluable participants of a cohort with at least two post-baseline evaluable tumor assessments, the recruitment of participants in that cohort will be stopped. If there are  $\leq 3$  confirmed responses in the first 20 evaluable participants of a cohort, the recruitment of participants in the cohort will be stopped. There will be no pause in enrollment during the interim analysis of the first 12 evaluable participants of a cohort, and the futility boundary will be adjusted based on the actual number of participants at each stage.

Interim futility monitoring will be implemented through the Bayesian Posterior Probability (BPP) approach with the prior distribution for ORR assumed to be Beta (0.5, 0.5). [Table 5](#) has the operating characteristics for futility of stopping at 12 and 20 participants.

If no response is observed in the first 12 participants of a cohort, there is an 89% posterior probability that the actual response rate is no more than 10%. If there are  $\leq 3$  responses in the first 20 participants of a cohort, there is a 70% posterior probability that the actual response rate is no more than 20%.

Jazz Pharmaceuticals, Inc.

JZP712-201 Statistical Analysis Plan - Protocol Amendment

2

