## **9.2. Secondary Efficacy Endpoints and Analyses**

### **9.2.1. Duration of Response (DOR)**

The investigator-assessed objective response will be further characterized by the DOR. DOR will be evaluated for responders (confirmed CR and PR) only.

DOR is defined as the time (months) from first confirmed response (CR or PR) to the date of the first documented tumor progression as determined using RECIST v1.1 criteria or death due to any cause, whichever occurs first.

The following censoring rules will be applied to DOR:

- Participants who do not progress or die will be censored on the date of their last evaluable tumor assessment.
- Participants who started a new anticancer therapy without a prior reported progression will be censored on the date of their last evaluable tumor assessment on or prior to the initiation of first subsequent anticancer therapy.

Jazz Pharmaceuticals, Inc.

JZP712-201 Statistical Analysis Plan - Protocol Amendment

2

- Participants who are lost to follow-up or discontinued from the study without a prior reported progression and without start of subsequent anticancer therapy will be censored on the date of their last evaluable tumor assessment on or prior to the date of loss to follow-up or study discontinuation.

A by-participant listing will be presented including actual cohort, best response, duration of response, whether the participant was censored for duration of response, and if so, the reason.

[REDACTED]

[REDACTED]

[REDACTED]

[REDACTED]

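### SAP 9.1.1 programs best overall response as the best timepoint response up to progression, with no confirmation step, which conflicts with the BOR window and the confirmed-response ORR in the same section

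*SAP*

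**What the plan says.** SAP 9.1.1 has three statements that should fit together.

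- **BOR, definition.** The window runs from first dose to documented progression, "or the date of subsequent anticancer therapy, death due to any cause, loss to follow-up, or study discontinuation, whichever occurs first". Protocol 9.4.2 uses the same five-event window.
- **BOR, derivation.** The next sentence says BOR will be programmed "as the best timepoint response that a participant achieves during the study", with a parenthesis limiting this to responses "recorded between the date of the first dose of study treatment and the date of objectively documented progression per RECIST v1.1". The ranking is CR, then PR, SD and PD. Neither the sentence nor the ranking mentions confirmation.
- **ORR.** "The ORR is defined as the proportion of participants whose BOR is investigator-assessed confirmed CR or PR using the RECIST v1.1".

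The section also promises a table of BOR categories (CR, PR, SD, PD, NE) and a by-participant BOR listing. Protocol 9.4.2 adds only that "BOR will be determined programmatically in the analysis of the study results", so the best-timepoint rule appears in the SAP alone.

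Elsewhere the plan consistently means confirmed response. Protocol Appendix 8 and both schedules of activities require a confirmatory assessment at least 4 weeks later. SAP 9.2.1 says "DOR will be evaluated for responders (confirmed CR and PR) only". The stage 1 rule in protocol 9.5 begins "If no confirmed response per RECIST v1.1 is observed in approximately the first 12 evaluable participants of a cohort", and the stage 2 rule in SAP 5.5 counts "confirmed responses in the first 20 evaluable participants of a cohort, the recruitment of participants in the cohort will be stopped".

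**The concern.** ORR is the primary endpoint and is defined through BOR, so the BOR derivation should deliver the confirmed count. The only operational rule in the SAP delivers the best single timepoint instead. Nothing says how a run of timepoint responses becomes a confirmed BOR: how an unconfirmed PR is classed, or what happens when a confirmed PR is followed by a CR that is never confirmed.

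Two things are at stake. The first is a BOR table and listing that disagree with the ORR reported beside them. The second arises only if ORR is computed from this derivation: a numerator that is off by a response, in a design whose thresholds turn on single responses.

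**Working it through.** **1. What the literal rule does to particular sequences.** Scans are every 6 weeks ± 7 days through Week 36, so consecutive in-window scans are at least 42 − 7 − 7 = 28 days apart. The next scheduled scan can therefore serve as confirmation.

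| Sequence | BOR by the derivation sentence | Confirmed BOR, five-event window |
|---|---|---|
| PR, PD | PR | SD (if the 35-day minimum is met) |
| PR, PR, CR, PD | CR (unconfirmed) | PR |
| SD, new therapy, PR, PR | PR | SD |

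The SD entry in the first row follows the convention proposed in the fix; the documents do not state one.

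**2. What happens to ORR depends on how the program is completed.**

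- *Confirmation applied correctly at the ORR step:* ORR is right for the first two rows, but PR, PD still sits in the BOR table as PR, so CR+PR exceeds the ORR numerator.
- *Confirmation tested only on the BOR category:* in PR, PR, CR, PD the CR is unconfirmed, so a participant with a confirmed PR could be dropped.
- *Confirmation omitted:* PR, PD is counted as a response.

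The loss and the gain thus come from different readings, not from one program.

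**3. What one response changes.** Clopper-Pearson limits are L = Beta⁻¹(α/2; x, n − x + 1) and U = Beta⁻¹(1 − α/2; x + 1, n − x). The plan's figures reproduce:

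- 4/20, 70% CI: 10.5% to 33.4%
- 7/35, 95% CI: 8.4% to 36.9%
- 8/35, 95% CI: 10.4% to 40.1%

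With the Beta(0.5, 0.5) prior, the posterior is Beta(0.5 + r, 0.5 + n − r). This gives P(θ ≤ 10%) = 0.892 at 0/12 and P(θ ≤ 20%) = 0.697 at 3/20, matching the stated 89% and 70%.

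Moving by one response:

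- 3/20 to 4/20: the 70% lower bound goes from 6.8% to 10.5%, and P(θ ≤ 20%) from 0.697 to 0.477.
- 7/35 to 8/35: the 95% lower bound goes from 8.4% to 10.4%.
- 0/12 to 1/12: P(θ ≤ 10%) goes from 0.892 to 0.520.

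**4. How often the BOR table would disagree with ORR.** The documents give no rate of unconfirmed response. Let u be the assumed chance that a participant has an unconfirmed CR or PR and no confirmed one, independently across participants, with ORR itself correctly confirmed. Then P(at least one mismatch) = 1 − (1 − u)ⁿ. For example, 1 − 0.95²⁰ = 0.642.

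| Assumed u | n = 12 | n = 20 | n = 35 |
|---|---|---|---|
| 2% | 22% | 33% | 51% |
| 5% | 46% | 64% | 83% |
| 10% | 72% | 88% | 97% |

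The last row is a high assumption. With a confirmed ORR of 10, 15 or 20%, it would mean that 10/20 = 50%, 10/25 = 40% or 10/30 = 33% of all responders are unconfirmed.

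**The case against.** The endpoint is already fixed. Both documents define ORR by confirmed response. SAP 9.2.1 starts DOR at the first confirmed response, so a confirmed-response variable has to be derived anyway. The n = 12 and n = 20 rules count confirmed responses directly, and the SAP version of the n = 12 rule asks for at least two post-baseline evaluable assessments. No text requires CR+PR in the BOR table to equal the ORR numerator, and the table shells are in a separate document. All of this stands, and it limits the point to the derivation sentence.

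The objection to the window is also largely right. The five-event definition is the preceding sentence, so the parenthesis may be shorthand. Death, loss to follow-up and study discontinuation leave no later on-study scans. Only subsequent anticancer therapy could matter, and rarely: the protocol's Schedule of Activities and section 7.1 stop scans at new therapy, while Appendix 8 alone continues them where feasible.

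Three stronger readings are tempting, and the documents do not support them.

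- *That the SAP changed the planned analysis while section 7.8 declares no change.* Protocol 9.4 leaves technical detail to the SAP, and the ORR definition is the same in both.
- *That the interim decisions are compromised.* They would be affected only if the count at a look were taken from this derivation.
- *That the binomial chance of landing exactly at a threshold measures the risk of a wrong decision.* It ignores whether an affected participant exists and whether the derivation is used for that count.

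What the objection does not supply is the missing algorithm. The word confirmed in the ORR sentence states the aim; the sentence that tells the programmer what to do produces something else.

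**Conclusion.** The derivation sentence in SAP 9.1.1 is wrong as written. It conflicts with the BOR window in the sentence before it and in protocol 9.4.2, and with the confirmed-response ORR in the same section. It should be corrected because it lies on the path to the primary endpoint.

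The direct consequence is limited: built literally, each unconfirmed CR or PR is tabulated and listed as CR or PR. How often that makes the table differ from ORR rests wholly on the assumed values of u. An error in ORR itself, in either direction, is conditional on how the program is completed. The intended endpoint is clear, and every stated boundary, interval and posterior probability stands.

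**What to change.** Replace the second BOR sentence in SAP 9.1.1 with wording such as:

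*BOR is the best confirmed response, using only assessments up to the earliest of documented progression, subsequent anticancer therapy, death, loss to follow-up and discontinuation from the study. CR or PR counts only if a repeat assessment 4 weeks or more after its first documentation confirms it. A confirmed PR followed by an unconfirmed CR has BOR = PR. An unconfirmed CR or PR is not counted as CR or PR; it is classed as SD if the 35-day minimum is met, otherwise as PD or NE according to later assessments.*

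Add that the ORR numerator equals CR+PR in the BOR table. The classing of unconfirmed responses is a proposed convention; neither document states one, so the sponsor should check it against the RECIST v1.1 guideline it cites.

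The cost is SAP wording and the programming specification. Sample size, boundaries and data collection are untouched.

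Separately, and not needed for this fix, protocol Appendix 8 should be reconciled with the Schedule of Activities and section 7.1 on scans after new anticancer therapy. With the five-event window in the SAP, the ORR count is settled whichever way that is resolved.
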